 - Stage of prostate cancer, treatments for prostate cancer, and recent serum PSA level
 - New cancer diagnoses
 - New autoimmune disorders
 - New hematologic or neurologic disorders
 - Other new medical diagnoses
 - Date of death if patient deceased

10. **Response Monitoring**

A. **Immunological Monitoring**

Blood will be collected by either peripheral blood draw (up to 150 mL) or leukapheresis (50-100 mL) pre-immunization, after the initial three sipuleucel-T treatments, and at quarterly intervals up to one year, for immunological monitoring. From the heparinized blood, peripheral blood mononuclear cells (PBMC) will be prepared by density centrifugation over Ficoll-Paque using standard techniques. PBMC will be used directly for analysis, and residual material cryopreserved in liquid nitrogen using 90% autologous serum collected at the time of blood draw, or 90% fetal calf serum, and 10% DMSO. Sera will be prepared from the red-top tubes and stored in aliquots at -80°C for antibody analyses. $\text{IFN}\gamma$ and granzyme B ELISPOT analysis, PAP-specific T-cell proliferation, flow cytometric assays of antigen-specific cytokine secretion, and ELISA tests for antigen-specific antibodies, will be the primary methods of analysis. The primary antigens tested will be PAP (experimental), PSA (negative control), and tetanus toxoid (positive control). The primary immune analysis will be conducted at the 6-month time point, and compared with the pre-treatment time point, and for patients to be evaluable for immune response (primary endpoint), blood (PBMC and serum) from this time point must be available for analysis. However, immune monitoring will be conducted at the other time points indicated in secondary analyses to evaluate kinetic measures of immunity, and evaluate whether durable immune responses of particular phenotypes are elicited and/or maintained. Assays may be conducted at the time of sample collection (fresh) and/or batched and performed at one time from multiple cryopreserved samples collected at different time points. Other methods of effector and regulatory T-cell response to PAP and other human tissue antigens may be used. Some assays may assess immune responses to the PA2024 (PAP-GM-CSF) fusion antigen or to GM-CSF.

A.1. **Quantitative assessment of PAP-specific CD8+ T-cell effector immunity**

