REPORTING AND RESPONSE DEFINITION: Results will be presented as the mean (+/- standard deviation) number of spot-forming-units (sfu) per 10^6 cells (frequency), calculated by subtracting the mean number of spots obtained from the no antigen control wells from the mean number obtained in the experimental wells, normalized to 10^6 starting PBMC, from 8-well replicate assays. Comparison of experimental wells with control, no antigen, wells will be performed using a two-sample t-test, with $p < 0.05$ (two-sided) defined as a significant antigen-specific T-cell response. A significant antigen-specific response resulting from immunization will then be defined as a PAP-specific response detectable at the 6-month post-treatment time point (or other post-treatment time point evaluated) that is significantly higher than to media only (as above), at least 3-fold higher than the mean baseline value, and with a frequency > 10 per 10^6 PBMC.

A.2. Assessment of PAP-specific memory T-cell immunity

Ability of T-cell lines to proliferate in response to antigenic stimulation: T-cell proliferation in response to antigen stimulation as a measure of memory T-cell responses will be assessed by a PKH26 dye dilution assay (see Figure 3). Specifically, PBMC will be labeled *in vitro* with PKH26 dye (Sigma, St. Louis, MO) according to manufacturer's recommendation. T-cell cultures with and without antigens will be established in replicates using 2×10^5 peripheral blood mononuclear cells (PBMC)/well, plated in 96-well round bottom microtiter plates (Corning, Cambridge, MA), in media consisting of RPMI 1640 (Gibco) and supplemented with L-glutamine, penicillin/streptomycin, β -mercaptoethanol and 10% human AB serum (ICN Flow, Costa Mesa, CA). Antigens may include 1 μ g/ml of a pool of peptide spanning the amino acid sequence of PAP, 2 μ g/ml PAP protein (Research Diagnostics Inc., Flanders, NJ), 2 μ g/ml PSA (Research Diagnostics Inc.), 250 ng/ml tetanus toxoid, and 2.5 μ g/ml phytohemagglutinin (PHA). After 6-7 days of culture at 37°C/5% CO $_2$, cell surface markers will be stained to characterize the T-cell phenotype and memory phenotype of proliferating cells (CD45RO, CCR7). Flow

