cytometry will be used to identify and enumerate CD3+CD4+ and CD3+CD8+ T cells co-staining for PKH26. The frequency of antigen-specific CD3+CD4+ and CD3+CD8+ T cells will be determined by determining the precursor frequency of PKH26+ events among CD4+ or CD8+ events (estimated from the number of cells and number of cell divisions by dye dilution using ModFit software, Verity Software House, Topsham, ME), and subtracting the mean precursor frequency of proliferating cells under media-only conditions.

REPORTING AND RESPONSE DEFINITION: Data will be reported as a mean and standard deviation of antigen-specific (PAP-specific) proliferative precursors per 10^6 PBMC using triplicate assessments for each antigen-stimulation condition. Comparison of experimental wells with control, no antigen, wells will be performed using a two-tailed Student's t test, with $p < 0.05$ defined as a significant antigen-specific proliferative T-cell response. A significant antigen-specific response resulting from immunization will then be defined as a PAP-specific response detectable at the 6-month post-treatment time point (or other post-treatment time point evaluated) that is significantly higher than to media only (as above), at least 3-fold higher than the mean baseline value, and with a frequency > 100 per 10^6 CD4+ or CD8+ T cells.

A.3. Assessment of antigen-specific antibody immunity

Enzyme-linked immunosorbent assay (ELISA) for the detection of antibodies responses to PAP:

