An immune response will be defined based on the detection of augmented numbers of PAP-specific effector (IFN γ -secreting and/or granzyme B-secreting) and/or memory (proliferating) T-cell immune response after immunization, using blood obtained at 6 months for the primary analysis compared with pre-treatment. Specifically, a positive antigen-specific response resulting from immunization will be defined as a PAP-specific response by two or more of these three tests detectable at the 6-month post-treatment time point that is significantly ($p < 0.05$, two-sided using a two-sample t-test) higher than to media only, at least 3-fold higher than the mean baseline value, and with a frequency > 10 per 10^6 PBMC, based on 8-well replicate assays (for ELISPOT-based assays) or triplicate assays (for proliferation analysis). Otherwise, a patient will be declared as an immune non-responder.

Immune response will be determined as a static time point at 6 months, and “durable” immune responses will also be determined by the presence of a PAP-specific immune response by the criteria above detectable at 3, 9, or 12 months after study entry.

C.2. Secondary Clinical and Immunological Endpoints

C.2.1. Time to Progression

Time to progression will be defined as a function of baseline time points in two ways:

- (1) *Time to progression from randomization*: Time elapsed from randomization until disease progression or death. If a patient doesn't experience a disease progression or death event before the end of the follow-up period, then the observation for this patient will be censored.
- (2) *Time to progression from 3 months post-randomization*: Time elapsed from the 3 months disease progression assessment until disease progression or death. If a patient doesn't experience a disease progression or death event before the end of the follow-up period, then the observation for this patient will be censored.

The rationale for defining time to progression as a function of baseline time points (date of randomization and 3-month disease assessment) is described in Section 6 (B).

C.2.2. Twelve-month Progression Free Survival Rate

The 12-month progression free survival rate will be defined as the proportion of patients progression free at the 12 month (post-randomization) disease assessment time point.

C.2.3. Overall Survival

Overall survival will be defined as the time interval from randomization to death from any cause or to the last follow-up in censored patients.

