The number of circulating tumor cells per million PBMC will be summarized in terms of medians and ranges, stratified by study arm and assessment time point. The nonparametric Wilcoxon Signed Rank test will be used to evaluate the effects of treatment on the number of circulating tumor cells within each study arm. The comparison of changes in the number of circulating tumor cells between study arms will be performed using the nonparametric, stratified, Wilcoxon Rank Sum test. Results will be presented graphically over time, and trends (increase, decrease, stable) will be assessed over time.

G.5.2. Analysis for evaluating PAP-specific antibody and T-cell immune responses following treatment with sipuleucel-T and DNA vaccine

PAP-specific antibody and T-cell immune responses, evaluated by multiple different measures described in Section 10.A, following treatment with sipuleucel-T and DNA vaccine will be summarized in tabular format.

G.5.3. Analysis for evaluating whether PAP-specific immune response is associated with prolonged (1 year) progression-free survival

Logistic regression analysis will be conducted to evaluate whether PAP-specific immune response is associated with prolonged (1-year) progression-free survival. The dependent variables will be 12-month progression free survival while treatment arm and PAP-specific immune responses (no vs. yes) will be included as covariates. The results will be reported in terms of odds ratios and the corresponding 95% confidence intervals.

G.5.4. Analysis for evaluating whether baseline immune responses (Th1 type or regulatory type) predict for immune responses elicited/augmented following treatment with sipuleucel-T +/- DNA vaccine

Logistic regression analysis will be conducted to evaluate whether baseline immune responses (Th1-type or regulatory type) predict for immune responses elicited/augmented following treatment with sipuleucel-T +/- DNA vaccine. 6-month and durable immune response at 3,6 or 12 months will be included as dependent variables in this analysis while treatment arm and baseline PAP-specific immune responses (no vs. yes) will be included as covariates. Odds ratios and the corresponding 95% confidence intervals will be reported.

G.5.5. Analysis for evaluating whether treatment elicits immunologic antigen spread to other prostate associated antigens

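### The proliferation test in the primary responder rule has two conflicting cut-offs on different denominators (Sections 12.C.1 and 10.A.2), and the plan does not say which one governs.

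*Combined protocol and SAP*

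**What the plan says.** Section 12.C.1 (Primary Immunological Endpoint) counts a patient as a responder when at least two of the three assays are positive at month 6. Each assay must exceed the media-only control (p < 0.05), be at least 3-fold above baseline, and clear one frequency floor: "and with a frequency > 10 per 10^6 PBMC, based on 8-well replicate assays (for ELISPOT-based assays) or triplicate assays (for proliferation analysis"). Everyone else is a non-responder. The same criteria define durable response.

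Section 10.A.1 gives the same floor for ELISPOT: "at least 3-fold higher than the mean baseline value, and with a frequency > 10 per 10^6 PBMC".

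Section 10.A.2 (proliferation) uses the same media-only and 3-fold conditions and names the same 6-month visit, but its floor differs: "at least 3-fold higher than the mean baseline value, and with a frequency > 100 per 10^6 CD4+ or CD8+ T cells". It derives the result as a "precursor frequency of PKH26+ events among CD4+ or CD8+ events", yet reports the data as "proliferative precursors per 10^6 PBMC using triplicate assessments".

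Section 10.A also refers to the primary analysis: "The primary immune analysis will be conducted at the 6-month time point, and compared with the pre-treatment time point". The reference from Section 12.G back to Section 10.A is in G.5.2, for a correlative tabulation: "evaluated by multiple different measures described in Section 10.A".

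**The concern.** Because two of three assays must be positive, the proliferation result decides responder status whenever exactly one ELISPOT is positive. If such a patient also passes the media-only and 3-fold conditions and has a frequency between the two floors, one section calls him a responder and the other a non-responder.

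There are two related gaps. Section 10.A.2 can be read as judging each subset on its own denominator, but 12.C.1 does not say how separate CD4+ and CD8+ results become one PBMC-based proliferation test. The choice of denominator may also change the 3-fold criterion if a subset's share of PBMC shifts between baseline and month 6.

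The responder classification feeds the primary comparison, the durable-response analysis and the logistic models in 12.G.5.3 to G.5.5. The trial is open-label, assays may be run fresh as samples arrive (Section 10.A), and study investigators can link coded specimens to subjects (Section 16.C). If the cut-off is settled only after results exist, the primary analysis contains a post hoc choice.

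**Working it through.** **Scope.** The floors in 10.A.1 and 12.C.1 agree for ELISPOT, so the conflict is confined to proliferation. The plan derives no figure from the proliferation floor, so there is none to reproduce. The sample size of 14 evaluable per arm (Section 12.F) is used only as an input.

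**Inputs.**
- 12.C.1 floor: 10 per 10^6 PBMC.
- 10.A.2 floor: 100 per 10^6 CD4+ or CD8+ T cells.
- Cells per proliferation well (10.A.2): 2 x 10^5 "peripheral blood mononuclear cells (PBMC)/well, plated in 96-well round bottom microtiter plates".
- f, the subset's share of PBMC: not in the documents. Every value below is an assumption.

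**Step 1: common scale.** The 10.A.2 floor per 10^6 PBMC is 100 x f. The 12.C.1 floor per 10^6 subset cells is 10 / f. Per well, 12.C.1 corresponds to 10 x 0.2 = 2 precursors and 10.A.2 to 100 x f x 0.2 = 20 x f.

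| Assumed f | 10.A.2 floor per 10^6 PBMC (12.C.1: 10) | 12.C.1 floor per 10^6 subset cells (10.A.2: 100) | 10.A.2 floor, precursors per well (12.C.1: 2) |
|---|---|---|---|
| 5% | 5 | 200 | 1 |
| 10% | 10 | 100 | 2 |
| 30% | 30 | 33 | 6 |
| 60% | 60 | 17 | 12 |

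The floors coincide only at f = 10%. Above that 10.A.2 is stricter; below it 12.C.1 is. For example, at f = 30% a frequency of 20 per 10^6 PBMC is 20 / 0.30 = 67 per 10^6 subset cells, which passes 12.C.1 and fails 10.A.2.

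**Step 2: 3-fold criterion.** Fold per PBMC = fold per subset cell x (f at month 6 / f at baseline). If f falls from 40% to 30%, a 3.5-fold rise per subset cell becomes 3.5 x 0.30/0.40 = 2.6-fold per PBMC and fails; passing would need 3 x 0.40/0.30 = 4.0-fold. If f rises from 30% to 40%, 3 x 0.30/0.40 = 2.25-fold is enough.

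**Step 3: combining subsets under 12.C.1.** With CD4+ and CD8+ frequencies of 6 and 6 per 10^6 PBMC, neither exceeds 10, but their sum of 12 does. The rule does not say which applies.

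**Step 4: what one patient is worth.** Each reclassified patient moves an arm's rate by 1/14 = 7.1 percentage points. Unstratified one-sided Fisher, 14 per arm:
- 4 vs 10 responders: p = 0.0285
- 4 vs 9: p = 0.0642
- 5 vs 10: p = 0.0642

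One patient in either arm carries this result across the one-sided 0.05 level. The planned test is stratified and exact (12.G.3), so these p-values are approximate.

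**The case against.** The strongest reply is that 12.C.1 governs. It carries the primary-endpoint heading and is the only place with the two-of-three rule and the non-responder default, whereas 10.A.2 is an assay-level definition that also serves other visits. A statistician working from Section 12 alone would apply one floor. That is a reasonable inference, but the plan never states it. Section 10.A.2 writes its own 6-month response definition, and Section 10.A speaks of the primary analysis. Nor can the PBMC floor be confined to ELISPOT, because 12.C.1 names the triplicate proliferation assay in the same sentence. Precedence would also leave the CD4+/CD8+ question open.

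Several narrower objections have force:
- Section 10.A.2 reports per 10^6 PBMC, so the 3-fold criterion may share a denominator in both sections. Step 2 is a conflict only if the fold is taken per subset cell.
- No passage proposes summing the subsets; the 6-and-6 case is constructed to show the gap.
- The assay estimates precursors by dye-dilution modelling, so the per-well figures restate the conversion and are not observed counts.
- The Fisher pair shows what one patient is worth at this sample size. It does not show that any patient would be reclassified.
- This is a pilot, and a cut-off fixed without reference to arm adds no directional bias.

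These points limit the claimed effect. They do not remove the two floors.

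**Conclusion.** The concern holds. A decision threshold in the primary responder rule has two values on two denominators, and the same patient can be classified differently under each. Expressed per 10^6 PBMC, the 10.A.2 floor is half the 12.C.1 floor at an assumed f of 5% and six times it at 60%.

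How often the rules would disagree is unknown, because the documents give neither f nor the distribution of proliferation frequencies. The frequency floor matters mainly for patients with exactly one positive ELISPOT who meet the other proliferation conditions and fall between the floors. No direction of bias is claimed.

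This should be fixed before scoring: the primary rule must give one answer per patient, and with 14 per arm a single patient can decide a borderline result.

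**What to change.** Before samples are scored, and without reference to arm, amend 10.A.2 and 12.C.1 to one proliferation cut-off on one denominator, used for both the frequency floor and the 3-fold criterion.

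One way is to list the cut-offs by assay in 12.C.1: more than 10 per 10^6 PBMC for each ELISPOT, and the 10.A.2 threshold for proliferation, with 10.A.2 then reporting in that unit. Keeping the PBMC floor for proliferation would also resolve the conflict if 10.A.2 is changed to match.

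In either case, 12.C.1 should say how CD4+ and CD8+ results count toward the one proliferation test: either subset alone, a named subset, or a sum. Report the primary comparison under the other cut-off as a sensitivity analysis.

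The cost is wording in two sections and one extra table, with no new samples or assays.

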CT abdomen/pelvis ^e	X											X ^f	X	X	X ^g
Bone scan ^e	X											X ^f	X	X	X ^g
Leukapheresis		X ^h	X		X		X						X ^{h,i}		
Sipuleucel-T infusion				X		X		X							
Tetanus immunization		X													
DNA immunization – ARM 2 PATIENTS ONLY ^a									X	X	X	X	X	X	
Blood for CTC analysis		X							X			X	X	X	X
Blood for immune studies ^j		X							X			X	X	X	X ^k

Note: Grey regions indicate those tests or procedures or visits only applicable to subjects treated on Arm 2. Acceptable delays in study treatments or procedures may result in corresponding delays of subsequent visits. Annual long term follow up will occur for up to five years. See Section 9 for more details.

^a ARM 2 Only: Biweekly DNA immunization (#1-3) can be +/- 3 days; quarterly DNA immunization (#4-6) can be +/- 7 days from expected date determined from prior visit.

^b Study coordinator or research nurse review of systems, including ECOG PS

^c CBC with differential and platelets to be performed within 72 hours prior to leukapheresis (for Sipuleucel-T treatment) unless an event occurs that would require it be drawn sooner for safety considerations, or if required sooner per institutional requirements or MD discretion. A CBC result within 7 days prior to leukapheresis for research is ideal.

^d PSA measurements must be performed at the 3-month intervals defined, but can be more frequent if clinically indicated.

^e Radiographic studies (CT scans and bone scans) can be performed +/- 7 days of the study visit

^f Staging studies (CT and bone scan): scan progression between Screening and Month 3 will not be used to define radiographic progression for the purposes of this study and will not necessitate subjects to come off study. Patients should come off study at this time point only due to symptomatic progression requiring other treatment for prostate cancer.

^g Radiographic studies not required at off-study time point if subject already met time-to-progression endpoint and/or studies already performed within 1 month; scans otherwise performed every 12 weeks

^h Leukapheresis collected (+/- 7 days) for research, not preparation of sipuleucel-T product

ⁱ If leukapheresis is not able to be obtained at Month 6 visit, then up to 150 ml may be obtained via peripheral blood draw as an alternative.

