Evidence that the toxicity rate is excessive will be considered sufficient if the lower limits of the 90% one-sided confidence intervals for the estimates of the true toxicity rates exceed the toxicity limits defined above (i.e., 20% for Grade 3 events and 10% for Grade 4 events), after the first 5 patients have been accrued. Operationally, this will occur if any of the following events occurs within a study arm: Grade ≥ 3 events (or Grade >1 autoimmune events) are present in at least 3 out of 5, 4 out of 9 (or less), 5 out of 13 (or less), or 6 out of 15 (or less) of the subjects accrued (within a study arm). Furthermore, accrual will be temporarily suspended if any of the following events occur: Grade 4 events are present in at least 2 out of 5, 3 out of 11 (or less), or 4 out of 15 (or less) of the subjects accrued (within a study arm).

If one of these thresholds is reached, accrual will be temporarily suspended and the study will be reviewed by the UW DSMC (data and safety monitoring committee) to consider safety and dose modifications with respect to treatment arm. Once the study is suspended, it would only be reopened if modifications could be made, and approved by the DSMC and the UW-IRB, to assure that patient safety is reestablished. If not, the study would be closed.

B. Endpoints

Patients will come off study at the time of radiographic disease progression, with progression being defined only AFTER the first 3-month staging evaluation, at the time of undue toxicity (as defined below), or at the discretion of the patient and treating physician that other therapies for prostate cancer are warranted. Patients should be discouraged from discontinuing protocol treatment for PSA rise only. Patients will continue to have blood drawn for immune studies, as per study calendar, up to one year after screening, even if off study prior to that time. The 6 month visit, in particular, is important to collect for the purpose of endpoint analysis. Subjects who have not come off study earlier for these reasons will come off study at the end of the one-year treatment period.

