The primary endpoint of the trial will be an immunological endpoint – the detection of augmented numbers of PAP-specific effector (IFN γ -secreting and/or granzyme B-secreting) and memory (proliferating) T-cell immune response after immunization, using blood obtained at 6 months for the primary analysis compared with pre-treatment. Immune response will be determined as a static time point at 6 months, and “durable” immune responses will also be determined by evaluation at 3, 9, and 12 months after study entry.

All subjects will undergo radiographic imaging (CT of abdomen and pelvis and bone scan) prior to treatment, and at 3-month intervals (or as clinically indicated). Radiographic disease progression will be defined using both RECIST 1.1 and PCWG2 published criteria [49], as detailed in Section 7. Based on the prior trials leading to the approval of sipuleucel-T, and because immune therapies are expected to require up to several months before radiographic responses or stabilization might be observed, the radiographic studies obtained at 3 months will not be used to define progression, rather will be used as the baseline for future comparison. That is, while baseline studies will be obtained prior to study registration, and radiographic progression may be expected in 50% of patients at 3 months, this will not be used to define progression necessitating patients come off study, rather disease progression occurring after this initial 3-month period. Time to progression will be determined from registration for all subjects. 1-year progression-free survival will be calculated for each treatment arm, as well as the median progression-free survival.

PSA doubling times will be calculated from all available values obtained within 3-6 months from the same clinical laboratory (when feasible) prior to study enrollment, up to and including the baseline value, and used to determine a pre-treatment PSA doubling time. Similarly, a post-treatment doubling time will be calculated from all PSA values obtained beginning with the PSA value at day 1 and continuing until the end-of study (or 1-year) value.

7. Measurement of Effect

A. Malignant Disease Evaluation

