To assess objective response, it is necessary to estimate the overall tumor burden at baseline (for purposes of comparison, “baseline” imaging will be that obtained at 3-month time point) to which subsequent measurements will be compared. Measurable disease is defined by the presence of at least one measurable lesion.

All measurements should be recorded in metric notation by use of a ruler or calipers. The same method of assessment and the same technique should be used to characterize each identified lesion at baseline and during follow-up. All pre-treatment evaluations should be performed as closely as possible to the beginning of treatment and not more than four weeks before registration.

The term evaluable in reference to measurability will not be used because it does not provide additional meaning or accuracy.

At baseline, tumor lesions will be characterized as either measurable or non-measurable.

NOTE: While progression will be documented from pre-treatment staging studies in all individuals, the intent of these measurements in this trial will be to determine whether “baseline” evaluation for immune-based treatments is preferable at a later time point after the therapy has been given the opportunity to exert an anti-tumor effect. Hence, the “baseline” evaluation for determining progression will be the staging studies performed at day 85 (3 months). Objective progression at Month 3 from the pre-treatment scans will not be used to alter treatment unless the

patient has symptomatic disease requiring other therapy and thereby needs to discontinue treatment.

1. Measurable

Lesions that can be accurately measured in at least one dimension (longest diameter to be recorded) as ≥ 20 mm (2.0 cm) with conventional techniques or as > 10 mm (1.0 cm) with **spiral** CT scan. For a lymph node to be considered pathologically enlarged and measurable, it must be ≥ 15 mm in short axis when assessed by spiral CT.

If the measurable disease is restricted to a solitary lesion, its neoplastic nature should be confirmed by cytology/histology.

Tumor lesions that are situated in a previously irradiated area are not considered measurable.

2. Non-Measurable

All other lesions, including small lesions [longest diameter < 20 mm (2.0 cm) with conventional techniques or < 10 mm (1.0 cm) with **spiral** CT scan], lymph nodes < 15 mm in short axis, and truly non-measurable lesions.

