All other lesions or sites of disease that do not meet the criteria for target lesions, including those on bone scintigraphy. Measurements of these lesions are not required, but the presence or absence of each should be noted throughout the study.

a. Complete Response (CR)

The disappearance of all nontarget lesions and undetectable PSA tumor marker levels. To be assigned a status of complete response, changes in tumor measurements must be confirmed by repeat assessments performed **no less than four weeks** after the criteria for response are first met.

b. Incomplete Response/Stable Disease (SD)

The persistence of one or more nontarget lesion(s) and/or the persistence of detectable serum PSA tumor marker levels. To be assigned a status of stable disease, measurements must have met the stable disease criteria at least once after study entry at a minimum interval of 12 weeks.

c. Progressive Disease (PD)

The appearance of one or more new lesion(s) and/or unequivocal progression of existing nontarget lesions.

NOTE: For lesions only detectable by bone scan, the appearance of ≥ 2 new lesions, with symptoms, will constitute disease progression. Without symptoms, and if no other evidence of disease progression (no progressive disease by PSA or measurable disease criteria), progression must be documented with repeat bone scintigraphy at least 6 weeks later demonstrating ≥ 2 new lesions. This is to eliminate the possibility of flair responses seen on bone scans.

3. Symptomatic Deterioration

Patients with a global deterioration of health status requiring discontinuation of treatment without objective evidence of disease progression at that time should be classified as having symptomatic deterioration.

4. PSA Progression

While PSA values will be collected, and PSA kinetics (PSA responses and maximal changes in PSA by waterfall plots) monitored as secondary endpoints, PSA rise will not be used to determine objective disease progression. Similar to the radiographic studies above, PSA progression or response will be defined using both pre-treatment (study entry) and 3-month values as baseline values.

- a. **PSA Complete Response:** Decrease in PSA to <0.2 ng/mL and confirmed with PSA measurement a minimum of four weeks later (confirmed PSA CR). There must be no evidence of radiographic progression.
- b. **PSA Partial Response:** Greater than or equal to 50% reduction in baseline PSA. There must be no evidence of radiographic progression.

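### Patients who leave for symptoms or other therapy without countable scan progression have no PFS event unless they die, so Kaplan-Meier 12-month PFS tends to be overstated

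*Combined protocol and SAP*

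**What the plan says.** **Event and censoring.** Sections 7.C.5 and 12.C.2.1 define time to progression in the same terms: "Time elapsed from randomization until disease progression or death", with a second version that starts at the 3-month assessment. A patient with neither event "before the end of the follow-up period, then the observation for this patient will be censored". The follow-up period is not defined. No rule covers going off study or starting another therapy.

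**What counts as progression.** Section 6.B uses RECIST 1.1 and PCWG2. Section 7.B.3 sets apart patients whose health declines so far that treatment must stop: those "without objective evidence of disease progression at that time should be classified as having symptomatic deterioration".

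**Month 3.** Study Calendar footnote f says that "scan progression between Screening and Month 3 will not be used to define radiographic progression for the purposes of this study", and then: "Patients should come off study at this time point only due to symptomatic progression requiring other treatment for prostate cancer". Section 6.B agrees that month-3 progression does not count and notes that "radiographic progression may be expected in 50% of patients at 3 months". The note in Section 7.A is less clear: "While progression will be documented from pre-treatment staging studies in all individuals", although the working baseline is the month-3 scan. Sections 12.G.4.1 and 12.G.4.2 plan one analysis from randomization and one from month 3.

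**Other ways to leave.** Section 6.B also lets patients leave "at the discretion of the patient and treating physician that other therapies for prostate cancer are warranted".

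**Estimator.** Section 12.C.2.2 defines the 12-month rate as a simple proportion. Section 12.G.4.1 estimates it by Kaplan-Meier, and Section 12.G.4.2 adds a stratified log-rank test.

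**The concern.** Patients who leave because symptoms require other treatment are likely to have a worse outlook than those who stay. If they are censored on leaving, Kaplan-Meier assumes that their later risk equals that of the patients who remain, so the censoring is informative. If they are instead kept at risk until death, any progression after they leave may go unseen, because the contact in Section 9.P is annual and includes no protocol scans. Both routes push the 12-month estimate up.

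Month 3 is the weak point. Scan progression found there is set aside, and footnote g waives the off-study scan if one was done within a month, so a patient who leaves at that visit need not be scanned again.

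The trial is open-label and leaving is partly discretionary. If departures differ between arms, the log-rank comparison can be biased in either direction. The logistic regression in Section 12.G.5.3 also takes 12-month PFS as its outcome and gives no status for these patients.

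**Working it through.** The documents give no PFS rate, PFS event count or departure rate, so there is no planned figure to reproduce. The 50% in Section 6.B is the expected month-3 scan progression, not the share who leave. The figures below only illustrate the mechanism.

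**Input from the plan.** 15 patients randomized per arm (Section 12.F).

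**Assumed inputs.** d patients leave at month 3 with no countable event. Among the rest there are 3, 3 and 2 progressions at months 6, 9 and 12 (8 in all), and nobody else is censored before month 12.

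**Leavers censored at month 3.** The risk set at month 6 is 15 − d. With d = 3:

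S(12) = (9/12) × (6/9) × (4/6) = 4/12 = 33.3%.

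**Leavers counted as events at month 3.** A first factor of 12/15 is added:

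S(12) = (12/15) × (4/12) = 4/15 = 26.7%.

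| Leavers d | Censored on leaving | Counted as events | Gap (points) |
|---|---|---|---|
| 1 | 6/14 = 42.9% | 6/15 = 40.0% | 2.9 |
| 2 | 5/13 = 38.5% | 5/15 = 33.3% | 5.1 |
| 3 | 4/12 = 33.3% | 4/15 = 26.7% | 6.7 |
| 4 | 3/11 = 27.3% | 3/15 = 20.0% | 7.3 |

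If all departures are at month 3, before any counted event, the ratio of the two estimates is 1/(1 − f), where f = d/15. It is 1.07, 1.15, 1.25 and 1.50 for f = 1/15, 2/15, 3/15 and 5/15. It does not hold exactly for later departures.

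**Leavers kept at risk, only death counted (d = 3).** With 0, 1, 2 or 3 deaths among them by month 12, S(12) is 7/15 = 46.7%, 6/15 = 40.0%, 5/15 = 33.3% or 4/15 = 26.7%. It falls to the composite value only if all three die.

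**Reading the censored figure.** 33.3% equals 5/15. It credits one of the three leavers with being progression-free at month 12, the same one-third share as among the 12 who stay (4/12). If leavers do worse than that, 33.3% is too high, and 26.7% is the floor, reached if all three progress or die by month 12.

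**Simple proportion (Section 12.C.2.2).** With all 15 in the denominator and leavers not counted as progression-free, the result is 4/15 = 26.7%, with no overstatement. That section does not say how leavers are to be counted.

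**Analysis from month 3.** A patient censored at the month-3 assessment has zero follow-up and contributes nothing, so the curve describes only those who stay.

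**The case against.** The strongest reply is that the plan never says that leavers are censored on leaving. Section 12.C.2.1 censors at the end of a follow-up period. Section 12.F promises at least 12 months of follow-up, and Section 9.P collects date of death, stage and treatments each year for up to 5 years, so a later death can count. This stands: censoring at the off-study date is an inference. It does not remove the problem, because keeping leavers at risk until death also tends to overstate PFS.

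Second, a reader might infer that every month-3 leaver lacks an event. The documents do not support that for the analysis from randomization. Section 7.A has progression from pre-treatment scans documented in everyone, and Section 12.G.4 plans that analysis separately, while footnote f and Section 6.B point the other way. The conflict is unresolved.

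Third, some later leavers will have a countable event. The off-study visit in Section 9.O includes CT and bone scan unless recently done, and Section 7.B.2 accepts two or more new bone lesions with symptoms without a confirmatory scan. What remains are those with no objective progression at exit, plus the month-3 group.

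Fourth, the eligibility criteria make early symptomatic exits less likely, and the effect is small beside sampling error: an exact 95% interval for 6 of 15 runs from about 16% to 68%. That limits the practical weight of the point. It does not justify leaving the rule unstated, since wide intervals do not correct a systematic shift.

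**Conclusion.** The concern holds in conditional form. A patient who leaves for symptomatic progression or other therapy without countable scan progression has no PFS event unless death is later recorded, and the plan states neither a censoring date nor a sensitivity analysis for such patients. Under either Kaplan-Meier reading, 12-month PFS tends to be overstated, provided that leavers do worse than those who stay.

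The size cannot be derived from the documents. The gap of 3 to 7 percentage points for 1 to 4 leavers rests on an assumed departure share, assumed progression counts, and all departures falling at month 3. A reader might go further and conclude that the plan censors these patients at the off-study date and overstates PFS by a known amount. The text sets no such date, and under the proportion in Section 12.C.2.2 the overstatement vanishes if leavers are not counted as progression-free.

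Bias in the log-rank test is possible, but only if departures differ by arm. PFS is secondary in a 30-patient pilot, and the primary immune-response analysis is untouched. The change is worth making because it is cheap.

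**What to change.** Keep radiographic PFS as the main definition, and amend Section 12 as follows:

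1. Define the follow-up period and the censoring date, and state the PFS status of patients who leave for symptomatic progression or other therapy.
2. Pre-specify, for 12.G.4.1 and 12.G.4.2, a sensitivity analysis in which going off study for symptomatic progression, or starting other prostate cancer therapy, is an event. Date it by the off-study date or by a therapy start date added to the case report form.
3. Report the number censored by reason and by arm.
4. Reconcile 12.C.2.2 with 12.G.4.1 (proportion versus Kaplan-Meier), and footnote f and Section 6.B with Sections 7.A and 12.G.4 (whether month-3 progression counts in the analysis from randomization).

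The cost is SAP wording, one extra analysis and possibly one date field: Section 9.P lists treatments for prostate cancer but does not ask for their start dates.
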